7.2. Screening and Critical Baseline Assessments

After written informed consent, screening assessments will be performed as outlined in the Time and Events Table (Section 7.1).

The following demographic parameters will be captured: year of birth, sex, race and ethnicity.

Medical/medication/family history will be assessed as related to the inclusion/exclusion criteria listed in Section 5.

Cardiovascular medical history/risk factors and smoking history (as detailed in the CRF) will be assessed at screening.

Procedures conducted as part of the subject's routine clinical management (e.g. blood count) and obtained prior to signing of informed consent may be utilized for Screening or baseline purposes provided the procedure meets the protocol-defined criteria and has been performed in the timeframe of the study.

7.3. Safety

Planned time points for all safety assessments are listed in the Time and Events Table (Section 7.1). Additional time points for safety tests such as vital signs, physical exams and laboratory safety tests may be added during the course of the study based on newly available data to ensure appropriate safety monitoring.

The investigator will be responsible for determining the clinical significance of any results that fall outside of the laboratory normal ranges.

In line with routine pharmacovigilance, an internal GSK Safety Review Team (SRT), which will include 203167 study team members, will review blinded safety data, including clinical laboratory parameters and adverse events, at appropriate intervals during the period of study conduct.

7.3.1. Adverse Events (AE) and Serious Adverse Events (SAEs)

The definitions of an AE or SAE can be found in [Appendix 4](#).

The investigator and their designees are responsible for detecting, documenting and reporting events that meet the definition of an AE or SAE.

7.3.1.1. Time period and Frequency for collecting AE and SAE information

- Any SAEs assessed as related to study participation (e.g., protocol-mandated procedures, invasive tests, or change in existing therapy) or related to a GSK product will be recorded from the time a subject consents to participate in the study up to and including any follow-up contact.

- AEs will be collected from the start of study treatment on Day 1 until the follow-up contact (see Section 7.3.1.3), at the time points specified in the Time and Events Table (Section 7.1).
- Medical occurrences that begin prior to the start of study treatment but after obtaining informed consent may be recorded on the Medical History/Current Medical Conditions section of the CRF.
- All SAEs will be recorded and reported to GSK within 24 hours, as indicated in [Appendix 4](#).
- Investigators are not obligated to actively seek AEs or SAEs in former study subjects. However, if the investigator learns of any SAE, including a death, at any time after a subject has been discharged from the study, and he/she considers the event reasonably related to the study treatment or study participation, the investigator must promptly notify GSK.

NOTE: The method of recording, evaluating and assessing causality of AEs and SAEs plus procedures for completing and transmitting SAE reports to GSK are provided in [Appendix 4](#).

7.3.1.2. Method of Detecting AEs and SAEs

Care will be taken not to introduce bias when detecting AEs and/or SAEs. Open-ended and non-leading verbal questioning of the subject is the preferred method to inquire about AE occurrence. Appropriate questions include:

- “How are you feeling?”
- “Have you had any (other) medical problems since your last visit/contact?”
- “Have you taken any new medicines, other than those provided in this study, since your last visit/contact?”

7.3.1.3. Follow-up of AEs and SAEs

After the initial AE/SAE report, the investigator is required to proactively follow each subject at subsequent visits/contacts. All SAEs, and non-serious AEs of special interest (as defined in Section 4.6.1) will be followed until resolution, until the condition stabilizes, until the event is otherwise explained, or until the subject is lost to follow-up (as defined in Section 5.4). Further information on follow-up procedures is given in [Appendix 4](#).

7.3.1.4. Cardiovascular and Death Events

For any cardiovascular events detailed in [Appendix 4](#) and all deaths, whether or not they are considered SAEs, specific Cardiovascular (CV) and Death sections of the CRF will be required to be completed. These sections include questions regarding cardiovascular (including sudden cardiac death) and non-cardiovascular death.

The CV CRFs are presented as queries in response to reporting of certain CV MedDRA terms. The CV information should be recorded in the specific cardiovascular section of the CRF within one week of receipt of a CV Event data query prompting its completion.

The Death CRF is provided immediately after the occurrence or outcome of death is reported. Initial and follow-up reports regarding death must be completed within one week of when the death is reported.

7.3.1.5. Regulatory Reporting Requirements for SAEs

Prompt notification by the investigator to GSK of SAEs related to study treatment (even for non- interventional post-marketing studies) is essential so that legal obligations and ethical responsibilities towards the safety of subjects and the safety of a product under clinical investigation are met.

GSK has a legal responsibility to notify both the local regulatory authority and other regulatory agencies about the safety of a product under clinical investigation. GSK will comply with country specific regulatory requirements relating to safety reporting to the regulatory authority, Institutional Review Board (IRB)/Independent Ethics Committee (IEC) and investigators.

Investigator safety reports are prepared for suspected unexpected serious adverse reactions according to local regulatory requirements and GSK policy and are forwarded to investigators as necessary.

An investigator who receives an investigator safety report describing a SAE(s) or other specific safety information (e.g., summary or listing of SAEs) from GSK will file it with the IB and will notify the IRB/IEC, if appropriate according to local requirements.

7.3.2. Pregnancy

- Details of all pregnancies in female subjects and female partners of male subjects will be collected after the start of dosing and until 30 days after the last dose.
- If a pregnancy is reported then the investigator should inform GSK within 2 weeks of learning of the pregnancy and should follow the procedures outlined in [Appendix 5](#).

7.3.3. Physical Exams

- A complete physical examination will include, at a minimum, assessment of the head, eyes, ears, nose, throat, skin, thyroid, joint, lymph nodes, cardiovascular, respiratory, gastrointestinal and neurological systems. Height and weight will also be measured and recorded.
- A brief physical examination will include, at a minimum assessments of the skin, lungs, cardiovascular system, and abdomen (liver and spleen).
- Investigators should pay special attention to clinical signs related to previous serious illnesses.

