4.6.1. Risk Assessment

Potential Risk of Clinical Significance	Summary of Data/Rationale for Risk	Mitigation Strategy
Investigational Product (IP) GSK2982772		
Central Nervous System (CNS) effects	
Non-clinical data: In the 4-week GLP toxicology study, CNS findings were observed in 4/12 monkeys which were administered 100 or 300 mg/kg/day. CNS findings included uncoordination, irregular gait, trembling, hunched appearance, and decreased activity. The clinical relevance of these findings in humans is not known. The NOAEL for this study was determined at 10 mg/kg/day.
 
In the 13-week GLP toxicology study, there were no CNS findings observed in monkeys administered 10, 30 or 100 mg/kg/day. The NOAEL for this study was determined at 30 mg/kg/day.
 
Clinical data: A First Time in Human (FTiH) study with single ascending and multiple ascending dose study has been performed in 67 healthy male volunteers to date (see Investigators Brochure (IB) [GlaxoSmithKline Document Number 2014N204126_01]. No drug-associated CNS adverse events were identified and no Serious Adverse Effects (SAEs) were reported.
	
Subject Selection:
 
 Subjects with known history of significant neurologic disorders including but not limited to progressive multiple sclerosis (MS), Amyotrophic lateral sclerosis (ALS), Alzheimer's and dementia will be excluded. Individuals with potentially increased susceptibility for neurologic effects will be excluded based on medical history at screening. 
Subject Monitoring:
 
 Subjects will be monitored for standard CNS-related adverse events.

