7.1. Time and Events Table

Procedures	Screening	Treatment Period												Early Withdrawal ¹⁴	Follow Up	Notes	
		Day 1	Day 8	Day 15	Day 22	Day 29	Day 36	Day 43 (week 6)	Day 50	Day 57	Day 64	Day 71	Day 78				
Screening Procedures																Visit windows Screening: up to 30d before Day 1. Treatment Period (except Day 1 & 85): ± 3d. Day 1 NA; Day 85 ± 2d. Early Withdrawal: NA Follow Up: 28d after last dose ± 3d	
Site Visit	X	X	X	X		X		X		X		X		X	X		
Phone call					X		X		X		X		X				
Safety Assessments																1. Full physical exam: height/weight at Screening, height not required at later timepoints. 2. Vitals: BP, HR, RR, temperature. ECG triplicate at Screening only. 3. Urinalysis not required on Days 29, 57 and 71. 4. If urine test is positive, confirmatory serum test must be performed. 5. Pre-dose 6. In Cohort 1, subjects must take study medication twice a day approx. 12h apart. In Cohort 2, subjects must take study medication three times a day approx. 8h apart. Exact time of dosing to be recorded in diary cards. On Days 43 and 85, subjects must not take medication at home in the morning. Subjects will complete pre-dose assessments and then will be administered their morning dose of medication at site on Day 43 only. On Day 85, subjects no longer dosed. 7. Diary card checked by site staff and new diary card dispensed at every study visit. 8. Blood samples for inflammatory	
Full physical exam ¹	X													X	X	X	
Brief physical exam		X ⁵		X		X		X ⁵		X		X					
12-lead ECG, vital signs ²	X	X ⁵	X	X		X		X ⁵		X		X		X	X	X	
Columbia Suicide Severity Rating Scale (C-SSRS)	X	X ⁵						X ⁵						X	X		
Hematology, chemistry, urinalysis	X	X ⁵	X	X		X ³		X ⁵		X ³		X ³		X	X	X	
FSH & estradiol (if applicable)	X																
Serum pregnancy (WCBP)	X																
Urine pregnancy test (WCBP only) ⁴			X ⁵	X	X		X		X ⁵		X		X	X	X		
Study Treatment																	
Randomisation		X															
Study medication ⁶		X	X														
Dispensing of study medication		X				X				X							
Dispensing of diary cards ⁷	X	X	X		X		X		X		X		X				
PROs/ Disease Assessments																	

Procedures	Screening	Treatment Period												Early Withdrawal ¹⁴	Follow Up	Notes
		Day 1	Day 8	Day 15	Day 22	Day 29	Day 36	Day 43 (week 6)	Day 50	Day 57	Day 64	Day 71	Day 78	Day 85 (week 12)		
Psoriatic Body Surface Area	X	X ⁵												X	X	
PASI, PGA, PLSS, Itch	X	X ⁵		X		X		X ⁵		X		X		X	X	
DLQI	X	X ⁵						X ⁵						X	X	
Photograph of lesions		X ⁵						X ⁵						X	X	

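### No physical examination scheduled between the first dose and Day 85 is required to include the neurological system, although CNS signs are a listed drug risk

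*Protocol*

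**What the plan says.** Protocol section 4.6.1 has a risk row headed "Central Nervous System (CNS) effects". Its non-clinical basis is the 4-week toxicology study: "CNS findings were observed in 4/12 monkeys which were administered 100 or 300 mg/kg/day". The same cell describes them: "CNS findings included uncoordination, irregular gait, trembling, hunched appearance, and decreased activity". It also reports no CNS findings in the 13-week monkey study at doses up to 100 mg/kg/day, and no drug-associated CNS adverse events in 67 healthy male volunteers. Besides exclusion of susceptible subjects, the stated mitigation is: "Subjects will be monitored for standard CNS-related adverse events".

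Section 7.3.3 defines two examinations. The complete one requires "assessment of the head, eyes, ears, nose, throat, skin, thyroid, joint, lymph nodes, cardiovascular, respiratory, gastrointestinal and neurological systems". The brief one is defined thus: "A brief physical examination will include, at a minimum assessments of the skin, lungs, cardiovascular system, and abdomen (liver and spleen"). The Time and Events Table (section 7.1) assigns one or the other to each visit. Its note 6 withholds the morning dose on Days 43 and 85 and adds: "On Day 85, subjects no longer dosed".

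**The concern.** The animal signs behind the listed risk are ones that an examiner sees: gait, coordination, trembling. The examination that would look for them systematically is not used at any planned visit while the subject continues on treatment. The brief form used there covers other organ systems.

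Safety and tolerability is the primary objective (section 3). Earlier repeat dosing lasted 14 days in 36 healthy men (section 4.6.1). This study doses patients of both sexes, up to age 75, for 84 days, and Cohort 2 has a predicted AUC about 50% above that of BID (section 4.5). Section 7.3.1.2 prefers open, non-leading questions for finding adverse events. That suits symptoms, but it is a weak instrument for a mild sign that the subject has not noticed. If some sites look for such signs and others do not, the comparison of active with placebo rests on uneven ascertainment in small arms (20 against 10, and 18 against 6).

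**Working it through.** **Step 1: which examination at which visit.** The table in section 7.1 was read by column position; the copies of it in Appendix 6 give the same positions. Content comes from section 7.3.3 and dose state from section 7.1, notes 5 and 6.

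| Visit | Examination | Neurological system required | Dose state |
|---|---|---|---|
| Screening | complete | yes | untreated, up to 30 days before Day 1 |
| Day 1 | brief | no | before first dose |
| Days 15, 29 | brief | no | on treatment |
| Day 43 | brief | no | on treatment, morning dose not yet given |
| Days 57, 71 | brief | no | on treatment |
| Day 85 | complete | yes | after the last dose, no morning dose |
| Early withdrawal | complete | yes | varies |
| Follow-up | complete | yes | 28 days after last dose |

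Examinations after the first dose and before Day 85: Days 15, 29, 43, 57 and 71, so 5. Number requiring the neurological system: 0 of 5. Day 8 is a site visit without a physical examination.

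**Step 2: the neurological baseline.** Day 1 carries the brief form, so the only required neurological baseline is Screening, up to 30 days before dosing.

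**Step 3: what Day 85 represents.** Inputs: a half-life of about 2 h (section 4.5) and dosing intervals of about 8 h (TID) and 12 h (BID) (section 4.2.2). Assumptions: the last dose was one interval before the visit, and decline is first order with absorption time ignored.

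Fraction remaining = 0.5^(hours since last dose / half-life)

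- TID: 0.5^(8/2) = 0.5^4 = 0.0625, about 6%
- BID: 0.5^(12/2) = 0.5^6 = 0.0156, about 1.6%

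If the half-life were 1.5 to 3 h (an assumed range), the fraction would be 2.5% to 16% for TID and 0.4% to 6% for BID. Day 85 is therefore a trough visit. The ±2-day window can move it to Day 83 or 84, but the morning dose is still withheld.

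**Step 4: which visits would add most.** Day 43 is also pre-dose, so an examination there sees the same trough state as Day 85. Note 6 does not withhold the morning dose on Days 15, 29, 57 and 71. Those four visits could detect a sign related to concentration that Days 43 and 85 might not.

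**Step 5: other monitoring during dosing.**

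- Adverse event enquiry at visits (7.3.1)
- Diary cards, and phone calls on Days 22, 36, 50, 64 and 78 (4.2.2)
- C-SSRS on Day 43, and alerting of families and caregivers to changes in behaviour (7.3.7)

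The C-SSRS is a suicidality scale. None of these is a structured look at gait, coordination or tremor.

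**The case against.** The strongest reply is that the protocol delivers what it promises. Section 4.6.1 commits to exclusion by history and to adverse event monitoring for CNS effects, and both are in place. This stands: a reader might infer that 4.6.1 and 7.3.3 contradict each other, and they do not. Nor does the position of CNS effects as the first row of the risk table amount to a stated ranking.

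The likelihood is also limited. The monkey findings came at 100 or 300 mg/kg/day in the 4-week study. The longer study, which is closer to this trial's duration, was clean up to 100 mg/kg/day, and predicted TID exposure lies within that observed at 120 mg BID. The lethargy, abnormal dreams and depressed mood reported in the first-in-human study are not motor signs. This lowers the priority.

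A reader might infer that CNS effects go unmonitored during dosing, or that a sign would surface only if the subject volunteered it. The documents do not support that. Besides the channels in Step 5, investigators are responsible for detecting events (7.3.1), the adverse event definition includes signs (Appendix 4), and a marked gait disturbance would be visible at any visit.

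A reader might also infer that Day 85 is a washout at which any CNS sign must have gone. That is not supported either. Day 85 is about one dosing interval after the last dose, and section 4.5 predicts that at Cmin on 60 mg BID about 90% of subjects still have more than 85% target engagement in blood. No section says that CNS signs track plasma level or reverse within hours.

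Finally, the brief examination is a minimum, and section 7.3 allows physical examination time points to be added. An optional check, however, is not collected in the same way at every site, so it cannot be compared between arms. That part of the reply does not remove the gap.

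**Conclusion.** The point holds as a gap between a named risk and the examination schedule. It is a design weakness, not an error of text. None of the five examinations after the first dose and before Day 85 requires a neurological component. The one required before follow-up in a subject who continues is at trough, and the only baseline is Screening. The consequence is limited: mild or concentration-related signs may be missed or recorded unevenly, while obvious ones would probably be caught.

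The count of 0 of 5 rests only on sections 7.1 and 7.3.3. The trough percentages rest on a 2 h half-life and a last dose one interval before the visit. Whether a CNS sign would be weaker at trough is unknown. Priority is low to moderate, and the change is worth making mainly because it is cheap.

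**What to change.** In section 7.3.3, add a short neurological component (gait, coordination, tremor) to the required content of the brief physical examination. It then applies at visits where that examination is already scheduled: Day 1 before dosing, which supplies a baseline on the day of first dose, and Days 15, 29, 43, 57 and 71. Days 15, 29, 57 and 71 add most. Record new findings as adverse events where they meet the Appendix 4 definition. If the sponsor prefers to leave the schedule as it is, section 4.6.1 should say why a risk identified from observable signs needs no scheduled neurological check during dosing.

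The cost is one line in 7.3.3, one CRF item and a few minutes per visit. No visit, dose or stopping rule changes. The downside is some incidental minor findings in both arms.

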7.3.4. Vital Signs

- Vital signs will be measured in a supine or semi-supine position after 5 minutes rest and will include temperature, systolic and diastolic blood pressure, pulse rate and respiratory rate.

7.3.5. Electrocardiogram (ECG)

- Triplicate ECGs will be obtained at screening and single 12-lead ECGs will be obtained at every other time point during the study using an ECG machine that automatically calculates the heart rate and measures PR, QRS, QT, and QTc (F or B) intervals. Refer to Section [5.4.4](#) for QTc withdrawal criteria and additional QTc readings that may be necessary.
- ECG is to be measured in a supine or semi supine position after 5 minutes rest.

7.3.6. Clinical Safety Laboratory Assessments

All protocol required laboratory assessments, as defined in [Table 3](#), must be conducted in accordance with the Laboratory Manual, and Protocol Time and Events Schedule.

Laboratory requisition forms must be completed and samples must be clearly labelled with the subject number, protocol number, site/centre number, and visit date. Details for the preparation and shipment of samples will be provided by the laboratory and are detailed in the laboratory manual. Reference ranges for all safety parameters will be provided to the site by the laboratory responsible for the assessments.

If additional non-protocol specified laboratory assessments are performed at the institution's local laboratory and result in a change in subject management or are considered clinically significant by the investigator (e.g., SAE or AE or dose modification) the results must be recorded in the CRF.

Refer to the laboratory manual for appropriate processing and handling of samples to avoid duplicate and/or additional blood draws.

All study-required laboratory assessments will be performed by a central laboratory.

NOTE: Local laboratory results are only required in the event that the central laboratory results are not available in time for either a treatment and/or response evaluation to be performed. If a local sample is required it is important that the sample for central analysis is obtained at the same time. Additionally if the local laboratory results are used to make either a treatment or response evaluation, the results must be entered into the CRF.

Haematology, clinical chemistry, urinalysis and additional parameters to be tested are listed in [Table 3](#).

Table 3 Protocol Required Safety Laboratory Assessments

Laboratory Assessments	Parameters			
Haematology	Platelet Count	RBC Indices:	WBC count with Differential:	
	RBC Count	MCV	Neutrophils	
	Hemoglobin	MCH	Lymphocytes	
	Hematocrit		Monocytes	
			Eosinophils	
			Basophils	
Clinical Chemistry ¹	BUN	Potassium	AST (SGOT)	Total and direct bilirubin
	Creatinine	Sodium	ALT (SGPT)	Total Protein
	Glucose ²	Calcium	Alkaline phosphatase	Albumin
	Triglycerides ²	Total Cholesterol ²	HDL cholesterol ²	LDL cholesterol ²
Routine Urinalysis	
 • Specific gravity • pH, glucose, protein, blood and ketones by dipstick • Microscopic examination (if blood or protein is abnormal) 			
Other Screening Tests	
 • HIV • Hepatitis B surface antigen (HBsAg) • Hepatitis B core antibody (HBcAb) • Hepatitis C (Hep C antibody) • QuantiFeron Gold test • T-spot (if QuantiFeron is indeterminant) • FSH and estradiol (as needed in women of non-child bearing potential only) • Urine hCG Pregnancy test (as needed for women of child bearing potential) ³. • Serum hCG (as needed for women of child bearing potential) to be done at screening and if urine test positive at other timepoints in study. • Estimated glomerular filtrate rate (eGFR) will be calculated using the CKD-EPI formula. 			
NOTES :	
 1. Details of Liver Chemistry Stopping Criteria and Required Actions and Follow-Up Assessments after liver stopping or monitoring event are given in Section 5.4.3 and Appendix 2. 2. No fasting required. Any abnormal result for glucose or lipids (non-fasted) may be repeated at the discretion of the investigator. 3. Local urine testing will be standard for the protocol unless serum testing is required by local regulation or ethics committee. 			

All laboratory tests with values that are considered clinically significantly abnormal during participation in the study should be repeated until the values return to normal or baseline. If such values do not return to normal within a period judged reasonable by the investigator, the etiology should be identified and the sponsor notified.

